6.1.1. Storage

Bottles of PTI-125 tablets should be stored at controlled room temperature, $20-25^{\circ}$ C (68-77° F) and protected from light and moisture.

6.1.2. Drug Accountability

The Investigator will be responsible for monitoring the receipt, storage, dispensing and accounting of all study medications according to site SOPs. All invoices of study medication shipments must be retained in the site study file. Accurate, original site records must be maintained of drug inventory and dispensing. All records must be made available to the sponsor (or designee) and appropriate regulatory agencies upon request.

6.2. ADMINISTRATION AND DOSING REGIMEN

Patients will be randomized to receive placebo (20 patients) or 50 mg PTI-125 b.i.d. (20 patients) or 100 mg PTI-125 b.i.d. (20 patients). Study drug should be taken 1-2 h before or after a meal.

6.3. CONCOMITANT MEDICATIONS

Use of prescription or non-prescription medications will be recorded during the study. Chronic medications must be stable for 3 months.

7. STUDY PROCEDURES

Appendix A presents the Schedule of Activities.

Prior to any study-related activities, the Informed Consent Form must be signed and dated by the patient or legal representative and the caregiver. The format and content of the Informed Consent Form must be agreed upon by the Principal Investigator(s), the appropriate IRB and the Sponsor (or designee). The signed and dated Informed Consent Form must be retained by the Investigator in the subject's file.

7.1. LIVER CHEMISTRY STOPPING CRITERIA

Liver chemistry threshold stopping criteria have been designed to assure patient safety and to evaluate liver event etiology during administration of Study Drug. Administration of Study Drug will be discontinued if any of the following liver chemistry stopping criteria occurs:

- ALT or AST $\geq 2.5 \times ULN$.
- ALT or $AST \ge 2 \times ULN$ and total bilirubin $\ge 2 \times ULN$. Note: Serum bilirubin fractionation should be performed if total bilirubin is $\ge 2 \times ULN$.
- ALT or $AST \ge 2 \times ULN$ if associated with appearance or worsening of a rash or hepatitis symptoms (fatigue, nausea, vomiting, right upper quadrant pain or tenderness, fever, rash or eosinophilia).
- ALP or GGT \geq 2.5 x ULN.

In the event of discontinuation due to liver abnormalities, the patient will be appropriately investigated to determine the potential cause.

7.2. EVALUATIONS BY VISIT

Follow-up visits can be scheduled +/- two (2) days from the actual Study Day number. Please notify Sponsor of changes so that the biomarker lab is aware of whole blood sample shipments.

7.2.1. Screening Visit 1 (No longer than 30 days prior to Day 1)

The following will be completed in the first screening visit:

- Informed Consent.
- Review of Inclusion and Exclusion Criteria
- Medical history
- Review of concomitant medications
- MMSE evaluation
- Columbia Suicide Severity Rating Scale (C-SSRS)
- Physical examination, including measurement of vital signs (blood pressure, temperature, pulse and respiratory rate), height, weight
- A 12-lead ECG (5-min supine)
- Laboratory assessments, including serum chemistry, hematology, urinalysis, and screens for HCV, HIV and HBsAg.
- Urine drug screen.

7.2.2. Screening Visit 2 (If all Screening Visit 1 criteria are met)

- Cambridge Cognition testing (conducted prior to CSF collection)
- CSF sample collection (5 mL)

CSF total tau/A β_{42} criterion (~1-week turnaround) must be met prior to Day 1.

7.2.3. Study Day 1 (Dosing Initiation)

Patients will come to the clinic in the morning. Prior to dosing, the following assessments will be conducted:

- Confirmation of inclusion/exclusion criteria
- Review of concomitant medications
- Vital signs (blood pressure, temperature, pulse and respiratory rate).
- Listen to heart and lungs
- Cambridge Cognition testing; the average of this result and that of the second screening visit will be taken as the baseline value.
- Blood sample collection for clinical laboratory tests
- Blood sample collection for PTI-125Dx and mTOR assessments (8 mL total)
- ECG

Patients will be administered Study Drug at least 1 h before or after a meal. The patient will be discharged 2 h later with their supply of Study Drug.

After dose on Study Day 1, the following assessments will be conducted:

- Vital signs (blood pressure, temperature, pulse and respiratory rate) at approximately 30 min, and 1 and 2 h post-dose.
- Adverse event monitoring

Clinic personnel will monitor the patients for the occurrence of any adverse events until patients are discharged from the clinic. Upon investigator judgment, patients will be discharged from the clinic with their supply of study drug until the next visit. The caregiver will be instructed to administer study drug twice daily at least 1 h before or after a meal. A dose can be up to 4 h late, but if a dose is missed, the next dose should NOT be doubled.

For all follow-up visits, patients will come to the clinic in the morning and will be instructed not to take their morning dose prior to coming to the clinic.

7.2.4. Day 7 Follow-up Visit

Patients will return to clinic on Study Day 7 before taking their morning dose.

On the morning of Study Day 7, within 30 min prior to dosing, the following assessments will be conducted:

- Blood sample collection for PK assessment (for C_{min})
- Clinical laboratory tests (blood and urine)

After dose, the following will be conducted:

- Vital signs (blood pressure, temperature, pulse and respiratory rate)
- Listen to heart and lungs
- Adverse event monitoring

7.2.5. Day 14 Follow-up Visit

Patients will return to clinic on Study Day 14 before taking their morning dose.

On the morning of Study Day 14, within 30 min prior to dosing, the following assessments will be conducted:

- Blood sample collection for PK assessment (for C_{min})
- Clinical laboratory tests (blood and urine)

After dose, the following will be conducted:

- Vital signs (blood pressure, temperature, pulse and respiratory rate)
- Listen to heart and lungs
- Adverse event monitoring
- ECG

7.2.6. Day 28 Follow-up Visit

Patients will return to the clinic in the morning on Study Day 28 and take their morning dose upon arrival.

After dose on Study Day 28, the following assessments will be conducted:

- Vital signs (blood pressure, temperature, pulse and respiratory rate)
- Adverse event monitoring

- Cambridge Cognition testing
- MMSE
- Columbia Suicide Severity Rating Scale (C-SSRS)
- ECG
- CSF sample collection (time post-dose to be recorded)
- Blood sample collection for PK (time post-dose to be recorded)
- Clinical laboratory tests (blood and urine)
- Blood sample collection for PTI-125Dx, mTOR and other biomarkers (8 mL total)

CSF sample collection (5 mL) on Study Day 28 will occur 1-2 h after dosing and after the MMSE and Cambridge Cognition testing have been completed. These samples will be tested for PTI-125 levels as well as the A β /tau Index, YKL40, inflammatory cytokines and other biomarkers.

Blood sample collection for PK assessment on Study Day 28 should be taken **as soon after the CSF draw as possible** to allow CSF to plasma ratio to be calculated.

7.2.7. End-of-study Follow-up

Patient will receive a follow-up phone call 7-14 days after the last dose. If needed, a follow-up clinic visit will be scheduled.

7.2.8. Unscheduled Visits and Discontinuation due to AEs

For unscheduled visits due to AEs, any assessments conducted will be at the discretion of the investigator and pertinent to the AE. If a decision is made to discontinue the patient from study drug, the Sponsor will be notified immediately. Restarting the patient on study drug will be a mutual decision by the investigator and the Sponsor.

7.3. LABORATORY ASSESSMENTS

7.3.1. Clinical Laboratory Tests

The following clinical laboratory tests will be performed at screening, Day 1 pre-dose, and at follow-up visits on Day 7, 14, and 28:

• Hematology: white blood cell (WBC) count with differential, red blood cell (RBC) count, hemoglobin, hematocrit, platelet count.

- Serum Chemistry: glucose, sodium, potassium, chloride, bicarbonate, calcium, phosphate, blood urea nitrogen (BUN), total bilirubin, creatinine, cholesterol, triglycerides, albumin, globulin, total protein, uric acid, alkaline phosphatase (ALP), alanine transaminase (ALT), aspartate transaminase (AST), gamma glutamyl transpeptidase (GGT), lactose dehydrogenase (LDH).
- Urinalysis: color, specific gravity, pH, protein, glucose, ketones and occult blood.

7.3.2. Preparation of Whole Blood Samples for biomarkers and APOE genotyping

Blood samples to be assessed in blood-based (lymphocytes or plasma) biomarkers, e.g. PTI-125Dx and mTOR, or genotyping (8 mL total) will be drawn into a Vacutainer® tube containing K₂EDTA. Collection will occur on Days 1 and 28. The tubes will be placed immediately on wet ice or in a refrigerator and shipped as whole blood, unfrozen, with cold gel packs (2-8°C) within 24 h to: [name], CUNY School of Medicine, [name]. Do not freeze, do not ship with dry ice, and do not ship whole blood samples on Friday.

7.3.3. Preparation of Plasma Samples for Pharmacokinetic Determination

At each blood collection for PK, blood samples (4 mL) will be drawn into a Vacutainer® tube containing K_2 EDTA. The tubes will be placed on ice. Within 30 min of collection, the blood will be centrifuged at approximately 1000 X G for 15 min, preferably at 4-5°C. Within 30 min of centrifuging, plasma (at least 1.5 mL) will be split into two aliquots, transferred to polypropylene tubes and stored at approximately -20°C or below until analysis.

At the end of the study or when advised by Sponsor, PK samples will be shipped frozen on dry ice to: Worldwide Clinical Trials Bioanalytical Sciences, [name] for bioanalytical analysis of PTI-125 with a validated assay. The second set of samples will be shipped separately once receipt of the first set is confirmed. One sample from each placebo subject will be analyzed. The timepoint will be selected to be near the C_{max} .

7.3.4. CSF assays

CSF samples should be split, with 2.5 mL shipped to [name] at CUNY and, for Day 28 only, an additional 0.5 mL shipped to Worldwide Clinical Trials (WCT). This 0.5 mL sample will be assayed for the PTI-125 analyte at WCT using a qualified assay. The remaining 2.5 or 2 mL will be retained at the study site frozen at -20°C or below until informed by the Sponsor.

CSF will be collected into 5 ml Screw-Cap LoBind Eppendorf® tubes (# 0030122356). When dividing into aliquots, the same tubes can be used or a 2 ml Sarstedt® Screw Cap Micro Tube Protein Low Binding (#72.694.600). CSF samples will be collected at the second screening visit and on Study Day 28.

The samples collected at screening and on Study Day 28 will be shipped **frozen on dry ice** (Monday – Wednesday) to [name], CUNY School of Medicine, [name] to be tested in biomarker assays including:

- Abeta
- Tau, ptau
- YKL40
- IL-6, TNF α and IL-1 β
- Neurogranin
- Neurofilament light chain

CSF samples collected at screening should be shipped to [name] upon collection; all Day 28 CSF samples can be held until end of study and shipped together per Sponsor instructions (2 mL samples), or for the 0.5 mL samples, to WCT along with plasma PK samples in one shipment.

8. EARLY DISCONTINUATION

Patients may choose to discontinue study drug or study participation at any time, for any reason, and without prejudice. Patients who discontinue may be replaced at the discretion of Sponsor.

The following must be completed and documented in the source documents and CRFs for all patients who discontinue the study early:

- The reason for early study discontinuation.
- Vital signs (blood pressure, temperature, pulse and respiratory rate), full physical examination, clinical laboratory tests, ECG, use of concomitant medications, and adverse events) should be obtained at discharge prior to release.
- Blood draw for PTI-125Dx, mTOR and other biomarkers
- MMSE
- Cambridge Cognition testing if not performed within the last 3 days

• CSF draw for biomarkers

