4. SUMMARY OF STUDY DESIGN

This is a Phase 2b, multi-center, randomized, double-blind, placebo-controlled, study of PTI-125 in mild-to-moderate AD patients, 50-85 years of age. Approximately sixty (60) patients will be enrolled into the study and randomized to one of three cohorts. Cohorts will receive placebo or PTI-125 at 50 or 100 mg b.i.d. (n=20 per group). Placebo or PTI-125 will be administered as coated tablets.

There will be two screening visits within 30 days of start of the study. Patients meeting initial screening criteria, including a Mini-Mental State Examination (MMSE) score ≥ 16 and ≤ 26 will return for a CSF draw at a second screening visit to confirm that the A β /tau Index is indicative of AD (final inclusion criterion). This CSF sample will also serve as baseline measurement for the YKL40 neuroinflammation and other potential CSF biomarker assays. Cambridge Cognition testing will be conducted at the second screening visit, Day 1, and at the end of the study. Patients will be assessed for suicidality via the Columbia Suicide Severity Scale (C-SSRS) during the first and last visits.

Patients will report to clinic the morning of Day 1. The following will be conducted prior to dosing: Cambridge Cognition testing, a full physical exam, an ECG and a blood draw for clinical labs and biomarkers (PTI-125Dx and mTOR). After dosing, patients will be monitored for adverse events and vital signs will be taken through 4 h. Patients will return to the clinic on Days 7, 14 and 28.

PK blood samples will be obtained prior to the first dose on Day 14 for C_{min} values. On Day 28, there will be a CSF draw after the last dose, and an additional PK blood sample will be obtained after this CSF draw for calculation of CSF/plasma ratio.

Blood draws for clinical laboratory testing will be performed at screening and on Days 1, 7, 14 and 28. Safety assessments of vital signs and listening to heart and lungs will be conducted at all visits. ECGs will be conducted on Days 7, 14 and 28.

Blood samples for testing in PTI-125Dx, the companion diagnostic/biomarker, mTOR activation and other potential blood-based biomarkers will be drawn on Day 1 and Day 28. The Day 28 blood sample will also be used for APOE genotyping. A CSF sample collection will be performed on Day 28 for neurogranin, neurofilament light chain, total tau, pTau (T181), A β_{42} , A β_{40} , YKL40, IL-6, IL-1 β , TNF α and other potential CSF biomarker assays as well as bioanalysis of PTI-125.

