6.2.2 Secondary Efficacy Analysis

CSF Biomarkers at Screening Visit 2 and Day 28 will be compared by using the two tailed paired t-test per each treatment group (Placebo, PTI-125 50 mg, and PTI-125 100 mg). The analysis will be performed based on the FAS population. The means, differences between means of Screening Visit 2 and Day 28, a 2 sided 95% CIs for the difference and the p-values from the t-test will be reported in the summary table.

Cambridge Cognition Test

Results will be summarized for subjects by treatment group. The summary and statistical analysis will be conducted using FAS population. The change from baseline on Day 28 will be analyzed by using a General Linear Model for the ANCOVA. The model will include the change from baseline as the dependent variable, the fixed effect of treatments, and baseline Cambridge cognition measurement as covariate. The means, Least Squares (LS) means, a 2 sided 95% confidence intervals (CI) for each LS means, differences between LS means, a 2 sided 95% CIs for each difference and the p-values from model effects will be reported in the summary table.

Dose Response Analysis 6.2.3

Nonlinear Emax model will be used in dose-response analysis. The model has the following form:

$$R_i = E_0 + \frac{D_i^N \times E_{max}}{D_i^N + ED_{50}^N} + \varepsilon_i$$

Where:

i = patient;

 R_i = The value of response for patient i (ex. Defined to be "Change form Baseline in A β_{42} at Day 28" should be repeated for the remaining CSF Biomarkers);

 D_i = Concentration of the drug in the plasma of the patient *i* at Day 28;

 E_0 = Basal response, when the concentration of the drug is zero or minimal;

 E_{max} = The maximum response attributable to the drug;

ED₅₀ = The concentration that produces half of maximum response;

N = The slope measures the change in response by moving from one concentration level to another;

 ε_i = The random error term for patient *i* – i.i.d and follows normal distribution with mean – 0 and variance.

Treatment group response will be predicted by applying the Emax model which intrinsically has 4 parameters to estimate (E0, Emax, ED50, N). This can be performed with "Proc NLIN" procedure in SAS by arbitrary specifying starting estimates for these parameters by treatment groups.

To assure optimal convergence of the procedure, the following starting estimates will be applied:

	Placebo	PTI-125 50mg	PTI-125 100mg
E ₀	0	Minimum response from observed data	Minimum response from observed data

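### The early-discontinuation visit repeats the Day 28 assessments except the C-SSRS and a drug-level sample paired with the CSF draw, and its 3-day cognition waiver can be met by the pre-dose Day 1 test

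*Protocol*

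**What the plan says.** Protocol Section 8 is worded as a requirement: "The following must be completed and documented in the source documents and CRFs for all patients who discontinue the study early". The list covers the reason for leaving, vital signs, full physical examination, clinical laboratory tests, ECG, concomitant medications, adverse events, "Blood draw for PTI-125Dx, mTOR and other biomarkers", MMSE, "Cambridge Cognition testing if not performed within the last 3 days" and "CSF draw for biomarkers". It names neither the C-SSRS nor a PK sample.

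Elsewhere:

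- **C-SSRS.** Protocol Section 4: "Patients will be assessed for suicidality via the Columbia Suicide Severity Scale (C-SSRS) during the first and last visits". Protocol Appendix A, SAP 2.1 and SAP Table 1 place it at Screening 1 and Day 28.
- **Drug level.** Protocol 7.2.6 asks for a PK sample as soon as possible after the Day 28 CSF draw, "to allow CSF to plasma ratio to be calculated". Protocol 7.3.4 provides the CSF drug-assay aliquot "for Day 28 only, an additional 0.5 mL shipped to Worldwide Clinical Trials (WCT"). In SAP 6.2.3 the exposure term of the Emax model is the "Concentration of the drug in the plasma of the patient" at Day 28.
- **Cognition.** Cambridge Cognition is scheduled at Screening 2, on Day 1 before dosing and on Day 28. Protocol 7.2.3 makes the Day 1 result part of baseline.
- **Early-termination data.** SAP 4.3.5 assigns them to the closest scheduled visit, or to the next available one if the closest already has valid data. SAP 4.3.4 rules out imputation.

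**The concern.** Section 8 keeps the burdensome parts of Day 28, including the lumbar puncture, and drops two light ones without giving a reason. Neither schedule table has an early-discontinuation column that would catch the gap.

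Two things are at stake. Patients who leave because of an adverse event are those in whom a structured suicidality check matters most, and a site working from the Section 8 list would not do one. And a patient who accepts a second lumbar puncture gives a biomarker response with no exposure measured at the same time, so that response can count in the primary analysis but not in the dose-response analysis, which serves the third study objective.

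The cognition waiver is a smaller matter: as worded, a baseline test can excuse the patient from a post-dose test.

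**Working it through.** The plan states no figure on this point, so the check sets the passages side by side and counts days.

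**1. Day 28 list (Protocol 7.2.6) against the Section 8 list**

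| Day 28 item | In Section 8? |
|---|---|
| Vital signs | Yes |
| Adverse events | Yes |
| Cambridge Cognition | Yes, with 3-day waiver |
| MMSE | Yes |
| C-SSRS | **No** |
| ECG | Yes |
| CSF | Yes, for biomarkers |
| PK blood | **No** |
| Clinical laboratory tests | Yes |
| Biomarker blood | Yes |

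Eight of ten are repeated and two are missing. The biomarker tube cannot stand in for the PK tube under the written handling rules: it travels as unfrozen whole blood (Protocol 7.3.2), whereas PK blood is centrifuged within 30 minutes (Protocol 7.3.3).

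**2. C-SSRS.** For an early leaver, the discontinuation visit is the last visit. Section 4 read that way requires the C-SSRS there. Section 8, Appendix A, SAP 2.1 and SAP Table 1 do not list it there. The C-SSRS is not among the safety endpoints in SAP 1.2.5.

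**3. Drug level.**

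*Which discontinuation CSF values become Day 28 values.* On-study visits are Days 1, 7, 14 and 28. The midpoint of the last two is (14 + 28)/2 = 21. A stop on Day 22 is 28 − 22 = 6 days from Day 28 and 22 − 14 = 8 days from Day 14, so Day 28 is closest from Day 22 on. For a stop between an attended Day 14 visit and Day 21, Day 14 is closest or tied. If that visit counts as holding valid data, the value moves on to Day 28. The SAP does not say whether validity is judged by visit or by assay, and CSF is not scheduled on Day 14.

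*Which concentrations already exist.* Pre-dose troughs are drawn on Days 7 and 14 (Protocol 7.2.4, 7.2.5, 10.3).

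| Stop day (nominal) | Troughs held | Plasma sample paired with discontinuation CSF |
|---|---|---|
| Before Day 7 | 0 | None |
| Days 7–13 | 1 | None |
| Days 14–27 | 2 | None |

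With the ±2-day visit window, the first trough can fall on Days 5–9.

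*Consequence.* The ANCOVA needs only the baseline and the change, so a reassigned CSF value can enter it. The Emax model needs a Day 28 plasma concentration, which this patient lacks and which is not imputed. The CSF/plasma ratio lacks both measurements.

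**4. Cognition waiver.** A stop on Day d is waived by the Day 1 test if d − 1 ≤ 3, that is d ≤ 4. Screening 2 comes about a week or more before Day 1, because the CSF result has a turnaround of about one week and must be in hand first. Even if Screening 2 fell on Day 0, the latest day Appendix A shows, it would still be pre-dose. So before Day 28 the only scheduled tests that can trigger the waiver are pre-dose, for stops through Day 4. From Day 5 until the Day 28 visit no scheduled test qualifies and the test is required.

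**5. Size.** One patient is 1/20 = 5% of an arm. No dropout rate is stated. At an assumed 5–15%, 0.05 × 60 = 3 to 0.15 × 60 = 9 patients leave early. Under 1:1:1 allocation about two thirds are on active drug: 3 × 2/3 = 2 to 9 × 2/3 = 6.

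**The case against.** A reader might infer that early leavers go home with no suicidality check, no drug concentration and no on-treatment cognitive measure. The documents do not support that.

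- **Suicidality.** Section 4 can be read to cover the discontinuation visit. Protocol 7.2.8 allows discretionary assessments at adverse-event visits, and Section 9.1 has patients withdrawn for an adverse event followed until it resolves or stabilizes. An omission from a list does not prove that nobody is assessed. Conversely, if the last visit in Section 4 simply means Day 28, nothing is contradicted. What stands is that the text bears both readings and the mandatory list follows the narrower one. The adverse-event enquiry is a non-specific question and the follow-up is a phone call, so neither replaces the C-SSRS.
- **Concentration.** Patients who stop after the first trough do have one. Only the sample paired with the CSF draw is missing. Part of the CSF is retained frozen at the site, so a CSF drug level might be recovered later; plasma that was never drawn cannot be. Caregivers record dosing times (inclusion criterion 13), so time since last dose can probably be reconstructed, but Section 8 does not ask for it as Day 28 does.
- **Cognition.** The MMSE is required at discontinuation without a waiver. An unscheduled test could satisfy the waiver, as could the Day 28 test if a patient withdraws during that visit. A score after one to three days of dosing says little about a 28-day effect, and the SAP cognition set needs Day 28 data in any case.
- **Dose-response.** Outside the reassignment cases, the response may not be in the Emax model at all, so the missing concentration is not what removes it. The model also has no term for time since dose: a washed-out concentration paired with a treated patient's response could mislead it. This stands, and it limits how a discontinuation sample should be used.

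Dropouts may be replaced, and drug level is largely moot on placebo. Both reduce the size of the problem.

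**Conclusion.** The point holds in a limited form. Section 8 omits two of the ten Day 28 assessments.

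1. The C-SSRS omission is an inconsistency with Section 4 and a safety-monitoring gap. It changes no planned analysis.
2. A discontinuation CSF value can count as a Day 28 biomarker response but has no paired plasma concentration for the Emax model and no CSF/plasma ratio. Reassignment is clear for stops from Day 22 and possible earlier, depending on how SAP 4.3.5 is read. The gap matters only in the active arms.
3. The cognition waiver is a wording defect with little analytic effect, confined to stops through Day 4.

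The number of patients affected is unknown. The range of 3 to 9 early leavers, about 2 to 6 of them on active drug, rests wholly on the assumed 5–15% dropout and equal dropout across arms.

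**What to change.** - Reconcile Protocol Sections 4 and 8, Appendix A, SAP 2.1 and SAP Table 1 so that the C-SSRS, already used in the trial, is listed at the early-discontinuation visit.
- Add to Section 8 one PK blood sample right after the CSF draw, extend the 0.5 mL CSF drug aliquot in Section 7.3.4 to that visit, and record the time since last dose.
- State in SAP 6.2.3 that a discontinuation pair enters the Emax model only if the patient was still on drug at the draw. State in SAP 4.3.5 whether validity is judged by visit or by assay.
- Reword the cognition waiver so that only a test done after the first dose, and within the 3 days, satisfies it.
- Add an early-discontinuation column to Appendix A and SAP Table 1.

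The cost is protocol and SAP wording, plus one questionnaire and one 4 mL tube per early leaver at a visit where blood and CSF are already taken. The downside is a few more minutes for a departing patient.
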